2.3. Follow-up and outcome measures

Functional outcomes were assessed with the patient-rated tennis elbow evaluation questionnaire (PRTEE). This outcome score consisted of 15 items related to three subscales, namely pain (5 questions), specific activities (6 questions), and daily activities (4 questions). The total score ranges between 0-100 points, 0 points designates the best functional outcome, whereas 100 points designates the worst functional outcome [12, 13]. To interpret PRTEE results, a minimum clinically important difference (MCID) value previously described by Poltawski et al. was used [14]. According to his study, a 37% decrease in PRTEE is considered a 'complete recovery' or clinically significant change. PRTEE was assessed before the injection (baseline values), on Day 15, Day 30, and Day 90, in the

same manner by the senior author. The same author performed follow-up and data collection. No patients received more than one injection in this clinical trial.

Hand grip strength (HGS) was measured with a digital hand dynamometer before and after injection in all patients. The senior author performed the measurements according to the American Society of Hand Therapists guidelines [15]. Since HGS varies according to factors such as height, weight, age, and gender, each patient's hand grip strength was calculated as a percentage increase from baseline.

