2.4. Sample size calculation

In our pursuit to determine the optimal sample size for our study on LE treatments utilizing PRTEE scores, we based our assumptions on several crucial parameters. We anticipated a 37% change in baseline PRTEE scores and considered a standard deviation (SD) of 10, drawing from previous studies. We adopted a conventional significance level (α) of 0.05 and aspired for a power of 0.90, applying the ANOVA testing methodology for three distinct treatment groups. Our computations indicated that to discern this 37% shift in PRTEE scores with the targeted power and significance level, a sample size of roughly 33 participants per group would be essential. Thus, given the three treatment groups in our research design, the aggregate sample size was estimated at 99 participants. However, taking into account a 20% dropout rate, the study included a total of 120 patients, with 40 patients in each group.

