2.5. Statistical analysis

Continuous variables were stated as mean and standard deviation, and categorical variables as percentages and frequency distribution. The conformity of the data to normal distribution was tested using the Kolmogorov-Smirnov test. For the comparison of continuous variables between the three groups, ANOVA was used for the data that fit the normal distribution, and the independent sample Kruskal-Wallis test was used for the data that did not fit the normal distribution. Categorical variables were compared using a chi-square test. Friedman test was used to assess the repeated measurements of the same group. A $p<0.05$ was set as a statistically significant alpha error.

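### Grip strength is compared across arms as percent increase with no baseline adjustment; ANCOVA on log grip would remove chance baseline imbalance and recover precision at almost no cost.

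*Combined protocol and SAP*

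**What the plan says.** Section 2.3 gives grip strength its own rule. "Hand grip strength (HGS) was measured with a digital hand dynamometer before and after injection in all patients", so a baseline value exists for everyone. The reason for rescaling is between-patient variation ("Since HGS varies according to factors such as height, weight, age, and gender"), and the remedy is that each patient's "hand grip strength was calculated as a percentage increase from baseline".

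Section 2.5 supplies the between-arm test: "ANOVA was used for the data that fit the normal distribution", and the "Kruskal-Wallis test was used for the data that did not fit the normal distribution". Neither test, as planned, carries a covariate. Neither section mentions ANCOVA, a baseline covariate or a log transformation.

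The timing of the grip readings is given only as "before and after injection in all patients". Section 2.3 ties Days 15, 30 and 90 to PRTEE; the abstract gives those days for follow-up in general. The sample size in section 2.4 concerns PRTEE alone, and no mean, SD, correlation or target difference is stated for grip.

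**The concern.** Dividing by the patient's own baseline puts whatever is temporary in that reading, such as measurement error or pain on the day, into the denominator. A patient who reads low for such a reason tends to show a large percent gain later, whatever the injection did. If one arm starts lower by chance, part of its apparent advantage is regression to the mean, and neither planned test removes it. The same mechanism adds noise, so the comparison is less precise than the collected data allow. Grip is one of only two outcomes named in section 2.3.

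**Working it through.** **Plan's own figure.** There is none for grip. The 33 per group (40 after dropout) in section 2.4 was derived for PRTEE; it is used here only as the number of patients available.

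**Assumed inputs.** Log-normal grip, mean 25 kg, SD 10, same log-scale spread at both visits; one arm 20% better than the other two; correlation r on the log scale from 0.5 to 0.9; alpha 0.05, three-arm F test with 2 numerator df.

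**Step 1: log-scale spread.** Variance σ² = ln(1 + (10/25)²) = ln(1.16) = 0.1484, so σ = 0.385.

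**Step 2: precision.** On the log scale, percent change corresponds to log follow-up minus log baseline, with variance 2σ²(1 − r). Baseline adjustment leaves σ²(1 − r²). The ratio is 2/(1 + r):

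- r = 0.5: 1.33, so 40 per arm does the work of 40/1.33 = 30
- r = 0.7: 1.18, so 40 does the work of 34
- r = 0.9: 1.05, so 40 does the work of 38

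**Step 3: power at 33 per arm.** The effect is δ = ln(1.2) = 0.1823, so δ² = 0.0332. With one arm different, the noncentrality is λ = 33 × δ² × (2/3) / variance. At r = 0.5, λ = 0.731/0.1484 = 4.93 unadjusted and 0.731/0.1113 = 6.57 adjusted. The noncentral F distribution then gives 48% and 61%. This ignores the small cost of estimating the baseline slope. Simulating percent change itself (3,000 replicates per setting) gives:

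| r | Closed form: log ratio / log ANCOVA | Simulated: percent change / log ANCOVA |
|---|---|---|
| 0.5 | 48% / 61% | 47% / 60% |
| 0.7 | 72% / 79% | 70% / 77% |
| 0.8 | 88% / 91% | 88% / 91% |
| 0.9 | both above 99% | about equal |

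**Step 4: chance imbalance.** With 40 per arm, the SE of a difference in mean log baseline is 0.385 × √(2/40) = 0.086. A 10% lower baseline is ln(1/0.9) = 0.105, or 1.2 SE, which is an ordinary chance difference. With no treatment effect, the low arm's follow-up-to-baseline ratio is raised by (1/0.9)^(1 − r) − 1:

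- r = 0.5: 5.4 percentage points
- r = 0.7: 3.2
- r = 0.9: 1.1

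**Step 5: false positives.** In a null simulation (40 per arm, 3,000 replicates), rejection rates were 4.6% for ANOVA and 4.4% for Kruskal-Wallis on percent change, and 5.0 to 5.1% for ANCOVA. All are close to 5%.

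**Step 6: is skew the cause?** In one simulation of the same model at r = 0.5, 0.7 and 0.8, power was 47, 73 and 88% for ANOVA on percent change, 48, 74 and 88% for ANOVA on the unskewed log ratio, and 46, 71 and 86% for Kruskal-Wallis on percent change. Removing the skew recovers almost nothing, so the loss comes from leaving baseline out.

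**The case against.** The strongest defence is that percent change is valid here. Allocation is randomised, so baseline imbalance is zero on average and the type I error is nominal. The authors' reason is also partly sound: if sex, height and weight scale both readings in proportion, the ratio cancels them. What remains is regression to the mean, not body size. All of this stands.

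Size is the second line of defence. Nothing in the documents favours a correlation of 0.5 over 0.9, and at 0.9 there is nothing to gain in power. Grip did not size the trial either. This also stands, and it limits the point to a free improvement.

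A reader might infer more than the documents support:

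- **That the grip comparison is biased outright, or yields too many false positives.** The distortion is conditional on the imbalance that happens to occur.
- **That skew, or the normality pre-test that chooses between ANOVA and Kruskal-Wallis, damages the analysis.** Section 2.5 already has a rank-based fallback. Under the log-normal model the full two-stage rule has power within about 2 points of ANOVA alone. That finding depends on the model. If grip is instead taken as normal with a coefficient of variation of 0.40 (40 per arm, r = 0.7), skew does hurt ANOVA: 41% power against 65% for Kruskal-Wallis and 83% for log-scale ANCOVA. That model puts zero grip only 1/0.40 = 2.5 SD below the mean, and the documents give no grip distribution to support it.
- **That ANCOVA on grip in kg would serve equally well.** Under log-normal grip at r = 0.8 it has 88% power against 89% for percent change, so it gains nothing. Log-scale ANCOVA was at least as powerful as percent change in every setting run, apart from negligible differences where both were near 100%.

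**Conclusion.** The point holds as one of precision and conditional imbalance. The plan collects baseline grip, uses it as a divisor, and then compares arms without adjusting for it. The direction is secure for any correlation below 1 with similar spread at both visits. The size is not: under the stated assumptions the power loss is about 13 points at correlation 0.5, 7 at 0.7, 3 at 0.8 and none at 0.9. The analysis as planned is inefficient and exposed to chance imbalance, but it is not invalid. The PRTEE sample size is unaffected.

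**What to change.** In sections 2.3 and 2.5, make the between-arm grip analysis an ANCOVA of log follow-up grip on treatment arm and log baseline grip, at each follow-up visit where grip was measured. The authors should confirm which of Days 15, 30 and 90 those were, since section 2.3 does not say. Report adjusted arm differences with 95% confidence intervals, back-transformed to percent differences so that the clinical reading is kept. Retain percent change as a descriptive column only.

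The cost is about two sentences, with no new patients, visits or measurements. If results have already been seen, the adjusted analysis should be labelled as a later change.

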2.4. Sample size calculation

In our pursuit to determine the optimal sample size for our study on LE treatments utilizing PRTEE scores, we based our assumptions on several crucial parameters. We anticipated a 37% change in baseline PRTEE scores and considered a standard deviation (SD) of 10, drawing from previous studies. We adopted a conventional significance level (α) of 0.05 and aspired for a power of 0.90, applying the ANOVA testing methodology for three distinct treatment groups. Our computations indicated that to discern this 37% shift in PRTEE scores with the targeted power and significance level, a sample size of roughly 33 participants per group would be essential. Thus, given the three treatment groups in our research design, the aggregate sample size was estimated at 99 participants. However, taking into account a 20% dropout rate, the study included a total of 120 patients, with 40 patients in each group.

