Lateral epicondylitis (LE) is a common musculoskeletal disorder affecting the extensor tendons of the forearm, manifesting as pain on the lateral side of the elbow and functional limitation during daily activities. Despite its name suggesting inflammation, histopathological examinations of the tendon reveal non-inflammatory angiofibroblastic tendinosis, accompanied by neovascularization, disorganized collagen, and mucoid degeneration [1, 2]. Since tendon degeneration is the underlying pathology, an effective therapeutic approach should reverse the degeneration to regeneration, ensuring symptom relief without recurrence.

Although many treatments exist, a consensus on the optimal single treatment for LE remains elusive. Traditionally, injections have served as a preliminary measure before resorting to surgical interventions, especially in resistant cases. However, an increasing number of alternative injections have been described in recent literature [3]. Newer injection therapies, such as autologous blood (AB) injections and platelet-rich plasma (PRP), have gained prominence and found favor among orthopedic surgeons. Multiple studies have attested to the safety and efficacy of AB and PRP injections as treatment modalities [4-7]. However, corticosteroid (CS) injections continue to be among the most commonly employed treatments for LE. A significant drawback of CS injections is their high recurrence rate. Patients typically experience a swift recovery immediately after injection, which endures for about a month. Unfortunately, this transient relief—often referred to as the 'honeymoon period'—is short-lived, leading to a recurrence of symptoms. Such a response pattern is well-documented in existing studies [8]. Conversely, AB injection therapy tends to proffer a gradual yet consistent reduction in symptoms, boasting a recurrence rate markedly lower than that of CS. It is postulated that AB addresses the intrinsic degeneration of the tendon, with its restorative process inherently spanning a more extended period [9-11].

We hypothesized that a combination of CS and AB injection might offer a superior treatment for LE. This combination may provide a faster resolution of symptoms due to the initial action of CS and provide a lower recurrence rate due to the regenerative action of AB. The purpose of this randomized clinical trial is to test three different types of injection for the treatment of LE: (1) AB, (2) CS, and (3) their combination (AB+CS).

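### The plan expects 20% dropout but states no analysis population or missing-data method, so outcome-related loss that differs by arm could bias the Day 90 comparison in an unknown direction

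*Combined protocol and SAP*

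**What the plan says.** Section 2.4 arrives at 33 patients per group, 99 in all, and then allows for loss: "However, taking into account a 20% dropout rate, the study included a total of 120 patients, with 40 patients in each group". This is the only mention of dropout.

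Section 2.3 sets PRTEE assessments at baseline and Days 15, 30 and 90. Section 2.5 is the whole analysis plan. Between arms: "For the comparison of continuous variables between the three groups, ANOVA was used for the data that fit the normal distribution", with Kruskal-Wallis otherwise. Within arms: "Friedman test was used to assess the repeated measurements of the same group". Categorical variables go to a chi-square test. No section defines who is analysed, what happens to a missing score, or how sensitive the result is to dropout.

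The Introduction describes an early response to CS that lasts about a month: "Unfortunately, this transient relief—often referred to as the 'honeymoon period'—is short-lived, leading to a recurrence of symptoms". It expects clearly less recurrence with AB. Section 2.2 says that treatment is open to both patient and physician.

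**The concern.** Extra enrolment protects precision. It does not protect against bias when the patients who leave differ in outcome from those who stay, and differ in another way in another arm.

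That matters here because the trial's own rationale has the arms separating between Day 30 and Day 90. The hypothesis that the combination lowers recurrence rests on Day 90, the only visit after the first month. Patients know what they received, so both relapse and recovery could plausibly affect who returns.

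Because the plan is silent, the analysis set is left to software defaults, or to a choice made after the losses are known. The visit-wise comparisons and the within-arm time course may also describe different patients in the same report.

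**Working it through.** **1. The plan's figure.** Inputs from section 2.4: 33 per group, 20% dropout.
- Multiplying up: 33 × 1.2 = 39.6, rounded to 40 per group, 120 in all. This reproduces the plan.
- After 20% loss: 120 × 0.8 = 96, or 32 per group, against 99 planned.
- The text gives no baseline mean, so 33 cannot be derived from a 37% change and SD 10. A three-group ANOVA at α 0.05 and power 0.90 does give 33 per group at a standardised effect f of 0.365. At 32 per group and that f, power is about 0.89. Precision is not the problem.

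**2. What the named tests use by default.**
- ANOVA and Kruskal-Wallis: every patient with a value at that visit.
- Friedman, standard form: only patients with all four values. If each of the three follow-up visits were missed independently by 8% (an assumption), it would drop 1 − 0.92³ = 22% of patients.

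**3. Bias with two classes of CS patient (assumed relapse share, severity and loss rates).** Let a share p relapse and score D points worse at Day 90, with loss rates d₁ in relapsers and d₀ in the others. The relapser share among those observed is w = p(1 − d₁) / [p(1 − d₁) + (1 − p)(1 − d₀)], and the bias in the CS mean is (w − p) × D.
- Example: p = 0.5, D = 20, d₁ = 0.3, d₀ = 0.1. Then w = 0.35/0.80 = 0.4375 and the bias is −0.0625 × 20 = −1.25 points (CS looks better than it is).
- For p from 0.3 to 0.7 and D from 10 to 30: with equal loss (20% in both) the bias is 0; with 30% against 10% it is 0.5 to 1.9 points; with 40% against 0% it is 0.95 to 3.75 points.
- If the non-relapsers leave more often, w exceeds p and the sign reverses.

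**4. Effect on the test.** SD 10 and 20% loss are the plan's; the loss pattern is assumed. There are 40 per arm, 8 lost per arm and no true difference. Loss is random in AB and AB+CS. In CS, the 8 patients highest on a driver that correlates r with Day 90 PRTEE are lost. The large-sample bias is r × 10 × φ(z₀.₈)/0.8 = r × 3.5. The standard error of a pairwise difference is 10 × √(2/32) = 2.5 points.

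| r | Spurious CS advantage (points) | ANOVA rejection at nominal 5% |
|---|---|---|
| 0 | 0 | 5% |
| 0.3 | 1.0 | 6–7% |
| 0.5 | 1.7 | 10–11% |
| 0.7 | 2.4–2.5 | 16–17% |
| 1 (extreme bound) | 3.4 | 31–32% |

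A gentler model, in which the chance of loss in CS rises smoothly with worse PRTEE, gives 5.9%, 7.3% and 10.5% for odds ratios of 1.5, 2 and 3 per SD.

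The bias can also hide a real effect. If CS were truly 8 points worse at Day 90 than the other two arms (assumed), power falls from 91% with random loss to about 75% at r = 0.5 and about 65% at r = 0.7.

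**5. How far a repeated-measures model helps.** Using Day 30 in a likelihood-type estimate removes the bias when loss is driven by the observed Day 30 score. When loss follows the unseen Day 90 level (r = 0.5), the 1.7 points fall only to 1.6, 1.3 and 0.9 for assumed Day 30–Day 90 correlations of 0.3, 0.5 and 0.7. If relapse is unrelated to Day 30, the 1.7 points do not change.

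**The case against.** Allowing for dropout by enrolling more patients is normal practice and not in itself an error. A reader might infer from sections 2.4 and 2.5 that the plan chooses to analyse attenders only. It does not say so: it names tests and is silent on the population. What stands is the omission and the default that follows from it.

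A reader might also infer that the bias will favour CS. The documents predict recurrence after CS but nowhere predict that relapsing patients leave. They may be the ones who come back, while recovered patients stop attending, which would make CS look worse. Loss of slow AB responders would flatter AB. The AB+CS arm also contains the steroid, so selective loss in CS alone is a chosen contrast. Equal loss rates in relapsers and others give no bias at all.

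The sizes are modest beside the spread of about 7.7 to 8.9 points that 33 per group can detect at SD 10. At r = 0.3 the rejection rate barely moves.

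The Friedman test is a within-arm test, so its loss of incomplete patients does not bias the comparison between arms.

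All of this limits the claim but does not remove it. An unknown direction is a reason to fix the rule in advance.

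**Conclusion.** The point holds as an omission with a conditional consequence. The plan expects one patient in five to be lost, states no analysis population or missing-data method, and depends on a Day 90 comparison for which its own rationale expects recurrence to differ by arm. Loss that is related to outcome and differs by arm could bias that comparison either way, and extra enrolment does not remove the bias.

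Under the assumed patterns (SD 10, 20% loss, selective in CS only, r from 0.3 to 0.7), the spurious difference is about 1 to 2.5 points and the 5% ANOVA rejects about 6% to 17% of the time. The rate of about 31% belongs to the extreme bound and should not be read as an expectation. The documents support neither a statement that bias will occur nor one about its direction. The change is worth making because it is cheap and its absence leaves the analysis set open.

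**What to change.** **Section 2.5, main comparison.** Compare PRTEE in all randomised patients as allocated. Use a likelihood-based repeated-measures model with baseline and all available Day 15, 30 and 90 scores, in place of per-visit ANOVA or Kruskal-Wallis. State that the model assumes loss is explained by observed scores.

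**Section 2.5, sensitivity.** Shift the missing Day 90 scores over a stated range in both directions, separately by arm (for example up to 15 PRTEE points each way). This analysis, with any scores that can be retrieved, has to cover loss driven by unseen change after Day 30, because the model corrects that only in part. In the analysis of the 37% decrease, count missing patients as not improved as a sensitivity analysis only, since that assumption also runs one way.

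**Reporting.** Give loss and its reasons by arm and visit.

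**Section 2.3, only if follow-up is still open.** Follow every randomised patient to Day 90, and obtain a missed PRTEE remotely within a stated window. The text is in the past tense, so this may no longer be possible; the analysis changes do not depend on it.

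**Cost.** One extra model, somewhat wider reported uncertainty, a few reminder contacts, and possibly small differences between remote and clinic forms. No extra patients are needed.

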2.2. Treatment groups and randomization

After taking informed consent, patients were randomly allocated into three treatment groups (AB versus CS versus their combination) with sealed envelopes prepared by a computer-based random number generator. A total of 120 envelopes were divided into three equal groups, 40 patients in each group. Patients in the AB Group received 1 ml of autologous venous blood mixed with 2 ml of 2% prilocaine HCl, patients in the CS Group received 1 ml of 40 mg methylprednisolone acetate mixed with 2 ml of 2% prilocaine HCl, and patients in the Combined Group (AB+CS) received 1 ml of autologous venous blood, 1 ml of 40 mg methylprednisolone acetate mixed with 1 ml of 2% prilocaine HCl. Each group received an equal amount of (3 ml) injected material. Venous blood was collected from the antecubital fossa of the ipsilateral extremity. The senior author performed all injections, and neither the physician nor the patient was blinded to the treatment modality. The injection was administered in aseptic conditions, and the needle was introduced over the maximal tenderness point; the content of the syringe was injected at once to prevent further bleeding. All patients were instructed to abstain from heavy work, and no additional therapy, including NSAIDs or physiotherapy, was prescribed.

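### The enrolled number of 120 does not cover the stated 20% dropout: it leaves 32 per group against the plan's own figure of roughly 33, and covers at most 17.5%

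*Combined protocol and SAP*

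**What the plan says.** Section 2.4 sets out the sample size in three steps.

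- **Requirement per group.** For a three-group ANOVA with alpha 0.05 and power 0.90, it concludes that "a sample size of roughly 33 participants per group would be essential".
- **Total requirement.** It carries this forward: "the aggregate sample size was estimated at 99 participants".
- **Allowance for dropout.** It then states that, "taking into account a 20% dropout rate, the study included a total of 120 patients, with 40 patients in each group".

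Section 2.2 confirms the enrolled number and the equal allocation: "A total of 120 envelopes were divided into three equal groups, 40 patients in each group".

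The plan does not show the formula that takes 99 to 120. It does not define the dropout rate in any unusual way, for example as a percentage added to the required number.

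**The concern.** A dropout rate is a share of the patients enrolled. To have n patients left after a fraction d drops out, a trial must enrol n/(1 − d). The step from 99 to 120 looks too small for d = 20%, because 120 is only about 21% more than 99 (120/99 = 1.212), whereas a 20% loss needs 25% more (1/0.8 = 1.25).

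The dropout allowance is the only reason the plan gives for enrolling 120 and not 99. A reader who relies on section 2.4 would take it that 8 losses in each group still leave the number the plan calls essential. What is at stake is the accuracy of that stated tolerance and, to a small degree, the power that remains if dropout reaches the anticipated level.

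**Working it through.** **Inputs**

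- Required: 33 per group (given as approximate) and 99 in total (section 2.4)
- Dropout: d = 20% (section 2.4)
- Enrolled: 120, 40 per group (sections 2.2 and 2.4)
- Alpha 0.05, power 0.90, three-group ANOVA (section 2.4)

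**1. Reproducing the plan's figure**

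Multiplying by (1 + d): 33 × 1.2 = 39.6, rounded up to 40 per group, and 3 × 40 = 120. This is the stated number. The same step on the total gives 99 × 1.2 = 118.8, so 119. The stated N is therefore consistent with adding 20% to the requirement per group. As no formula is shown, this explanation is an inference.

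**2. What remains after 20% dropout**

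- Per group: 40 × (1 − 0.20) = 32, against 33
- Total: 120 × (1 − 0.20) = 96, against 99

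The shortfall is 1 per group and 3 overall.

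**3. Dropout that 120 does cover**

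1 − 33/40 = 7/40 = 17.5%. The total gives the same: 1 − 99/120 = 17.5%.

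**4. Enrolment that 20% dropout needs**

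- Total: 99/0.8 = 123.75, so 124
- Per group: 33/0.8 = 41.25, so 42, and 3 × 42 = 126 with equal groups

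**5. Effect on power**

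The one-way ANOVA F test with k = 3 groups of n has 2 and 3n − 3 degrees of freedom and noncentrality λ = 3n·f², where f is the standardised spread of the group means. The documents do not give f: "We anticipated a 37% change in baseline PRTEE scores and considered a standard deviation (SD) of 10" becomes an effect size only with a baseline mean and a pattern of group means, and neither is stated. The values of f below are therefore assumptions.

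| Assumed f | Meaning | Power, n = 32 | Power, n = 33 |
|---|---|---|---|
| 0.3632 | 33 per group gives exactly 90% | 89.0% | 90.0% |
| 0.3690 | upper end of the range in which 33 is the smallest n reaching 90% | 90.0% | 90.9% |
| 0.37 | just above that range | 90.2% | 91.1% |

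If 33 is the smallest n that reaches 90%, f lies from 0.3632 to just below 0.3690, and power at 32 per group lies between 89.0% and just under 90.0%. With no dropout, 40 per group gives 95.0% at f = 0.3632.

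**The case against.** The strongest reply is that the gap is too small to matter. The plan calls its figure approximate, one patient per group is within that hedge, and the loss of power is about one percentage point at most. With f = 0.37, 32 per group would already give 90.2%, so 120 enrolled would meet the power target after a 20% loss. This stands as far as it goes: a fall below 90% is not established. It does not remove the mismatch, because the plan carries the approximate 33 forward to a total of 99, and 96 is not 99. Nowhere does it say that 32 would be enough.

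A second reply is that the plan says only that a 20% rate was taken into account, not that 33 per group would remain after such a loss, and that adding 20% to 33 does give 40. That explains the number but does not justify it. A 20% dropout rate means a loss of one enrolled patient in five, and 40 per group does not absorb that loss.

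A third reply is that 33 itself cannot be reproduced, so correcting the allowance around it gives false precision. The premise is right, and that gap is the larger one. With SD 10 and assumed baseline means from 20 to 60 points, the number per group for 90% power runs from 36 down to 6 if one group differs from the other two, and from 48 down to 7 if the three means are evenly spaced. It is a separate point, however. The inconsistency here holds for the printed 33, 20% and 40, whatever produced the 33. The objection is a good reason to keep the word roughly in any corrected text.

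**Conclusion.** The concern holds. Section 2.4 states a dropout tolerance of 20%, but on its own figures 120 patients tolerate 17.5%. This conclusion needs no outside figure and only the ordinary reading of a dropout rate as a share of those enrolled.

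The consequence is minor. The loss of power relative to 33 per group is about one percentage point, for effect sizes at which 33 per group gives about 90%. Whether power would drop below the 90% target at 20% dropout cannot be settled from the documents. The point calls for a correction to the sample-size justification and does not put the design in doubt.

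**What to change.** Keep 120 and replace the dropout sentence in section 2.4 with wording such as:

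> With 40 patients randomised per group, the estimated requirement of roughly 33 per group (99 in total) is retained if dropout does not exceed 17.5% (7 patients) in any group. At 20% dropout, 32 per group (96 in total) remain.

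Give a power figure for 32 per group only if it is recomputed from the effect size actually used. Otherwise label it as about 89%, on the assumption that 33 per group gives exactly 90%.

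The cost is one reworded sentence and a stated tolerance that falls from 20% to 17.5%. The number enrolled, the randomisation and the analysis stay as they are. Keeping the 20% claim instead would need 124 patients, or 126 in equal groups, which is 4 or 6 more than the 120 envelopes prepared.
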